6.4. Windowing Conventions

Each visit will have ± 1 day window. No visit windowing will be applied during the analysis for patients that have completed the study, and therefore the data will be presented as per the visit reported in the database.

For the discontinued patients End of Study (EOS) visit will be windowed to the corresponding visit, based on the study day, for questionnaire, spirometry and rescue medication data. The rules for the windowing are as follows:

- For questionnaires that only happen at certain visits, windowing will only be done for those corresponding visits.
 - o For SGRQ-C and CAT:
 - Day 1 = Day 1
 - Week 2 = after day 1 and up to and including day 16
 - Week 4 = after day 16 and up to and including day 30
 - o For TDI and PGAC:
 - Week 2 = after day 1 and up to and including day 16
 - Week 4 = after day 16 and up to and including day 30
 - o For rest of the questionnaires requiring windowing:
 - Day 1 = Day 1
 - Week 1 = after day 1 and up to and including day 9
 - Week 2 = after day 9 and up to and including day 16
 - Week 3 = after day 16 and up to and including day 23
 - Week 4 = after day 23 and up to and including day 30
- For spirometry raw data and derived data that happens at every visit, windowing will be done as per the corresponding visits.
 - o Day 1 = Day 1

Document: ...\\Verona_Pharma\\RPL554\\BZA48916\\Biostatistics\\Documentation\\SAP\\Verona CO-205 SAP v1.0

Author: [REDACTED] Version Number: V1.0

Version Date: 05DEC2019

Template No.: CS_TP_BS016 Revision 5

Reference: CS_WI_BS005

Effective Date: 01Apr2018

- Week 1 = after day 1 and up to and including day 9
- Week 2 = after day 9 and up to and including day 16
- Week 3 = after day 16 and up to and including day 23
- Week 4 = after day 23 and up to and including day 30
- For spirometry derived data that only happen at certain visits, windowing will be done for the corresponding visits.
 - For morning trough:
 - Week 1 = after day 1 and up to and including day 9
 - Week 2 = after day 9 and up to and including day 16
 - Week 3 = after day 16 and up to and including day 23
 - Week 4 = after day 23 and up to and including day 30
 - For AUC_{0-12h}:
 - Day 1 = Day 1
 - Week 4 = after day 1 and up to and including day 30
- For rescue medication data, windowing will be done as per the corresponding visits.
 - Day 1 = Day 1
 - Week 1 = after day 1 and up to and including day 9
 - Week 2 = after day 9 and up to and including day 16
 - Week 3 = after day 16 and up to and including day 23
 - Week 4 = after day 23 and up to and including day 30

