16.4. Missing Data Methods for Efficacy Variables

Data for calculation of average (AUC) effects for FEV₁ will be imputed if the pre-dose is not missing. This will be done using the following method:

- ‘bounded’ missing data will use interpolation through the trapezoidal method described in section 16.2.1.1.2,
- ‘unbounded’ missing data will not be imputed
 - If last measurement is missing, then the AUC will be calculated up to the point where data is not missing, however if two or more last measurements will be missing, then the AUC will be set to missing.
 - If first measurement is missing, the AUC will not be calculated and set to missing.

For the analysis of responder on SGRQ-C and CAT missing responses will be treated as indicating non-responders in the analysis.

All other missing data, including for when pre-dose is missing, will not be imputed.

For the sensitivity and interim analysis missing data will be imputed using LOCF method. In cases where patient discontinues early and has spirometry data reported at the EOS visit, the following strategy explained below will be used.

1. Check the visit day at which EOS visit was performed against the following window for

Document: ...\\Verona_Pharma\\RPL554\\BZA48916\\Biostatistics\\Documentation\\SAP\\Verona CO-205 SAP v1.0

Author: [REDACTED] Version Number: V1.0

Version Date: 05DEC2019

Template No.: CS_TP_BS016 Revision 5

Reference: CS_WI_BS005

Effective Date: 01Apr2018

each visit:

- a. Day 1 = Day 1
- b. Week 1 = after day 1 and up to and including day 9
- c. Week 2 = after day 9 and up to and including day 16
- d. Week 3 = after day 16 and up to and including day 23
- e. Week 4 = after day 23 and up to and including day 30

2. Set the value for the corresponding visit, and any subsequent visits, to be the value from EOS. If the corresponding visit has a measurement already, then the next available visit must be used for EOS.
3. If there are missing values before the EOS corresponding visit, we would impute using LOCF in the usual manner.

In the case where patient discontinues early and did not have spirometry data recorded at the EOS visit, or cases of missing data for patients who did not discontinue early, LOCF will be applied in the usual manner.

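### SAP 6.4 counts a discontinued patient's End of Study AUC0-12h from any of Days 2 to 30 as Week 4, and the LOCF ANCOVA cannot test that choice because it uses the same value

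*SAP*

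**What the plan says.** SAP 6.4 applies visit windows only to patients who discontinue: "For the discontinued patients End of Study (EOS) visit will be windowed to the corresponding visit, based on the study day". Completers' data stay at the visit recorded in the database.

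The Week 4 windows in SAP 6.4 differ by measure:

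- **Every-visit spirometry (including peak and AUC0-3h) and morning trough:** Week 4 is Days 24 to 30. Earlier EOS visits go to Week 1, 2 or 3.
- **SGRQ-C, CAT, TDI and PGAC:** "Week 4 = after day 16 and up to and including day 30".
- **AUC0-12h:** Day 1 is Day 1, and "Week 4 = after day 1 and up to and including day 30". The stated principle is "For spirometry derived data that only happen at certain visits, windowing will be done for the corresponding visits".

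SAP 16.4 adds: "For the sensitivity and interim analysis missing data will be imputed using LOCF method". For a discontinued patient with EOS spirometry it lists five visit windows, the last being "Week 4 = after day 23 and up to and including day 30", and instructs: "Set the value for the corresponding visit, and any subsequent visits, to be the value from EOS". It has no separate window for AUC0-12h.

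SAP 16.5 applies this LOCF to an ANCOVA of AUC0-12h at Week 4, which it calls a key secondary endpoint. SAP 7.2 otherwise limits imputation to the calculation of the AUC itself.

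**The concern.** The secondary objective is AUC0-12h at Week 4. Under SAP 6.4, a patient who stops on Day 5 and performs a full spirometry session has peak and AUC0-3h placed at Week 1 and AUC0-12h placed at Week 4. One session thus carries two time labels three weeks apart.

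In effect this is a carry-forward inside the main analysis, a device the SAP otherwise keeps for the sensitivity and interim analyses. The estimated Week 4 difference becomes a mixture of four-week and earlier effects. The analysis that should reveal any dependence on this handling gives the affected patients exactly the same Week 4 number.

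**Working it through.** **1. Width of the window.** Days 2 to 30 are 29 days and Days 24 to 30 are 7. The 22 days from Day 2 to Day 23 (22/29 = 76%) count as Week 4 for AUC0-12h but not for the other spirometry measures.

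**2. Main and sensitivity values side by side.**

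| EOS day | Peak, AUC0-3h, trough (6.4) | AUC0-12h (6.4) | AUC0-12h Week 4 value under LOCF (16.4) |
|---|---|---|---|
| 2 to 9 | Week 1 | Week 4 | same EOS value |
| 10 to 16 | Week 2 | Week 4 | same EOS value |
| 17 to 23 | Week 3 | Week 4 | same EOS value |
| 24 to 30 | Week 4 | Week 4 | same EOS value |

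In every row the two analyses hold the same Week 4 number. The repeat of the MMRM on the per-protocol set (SAP 16.5) differs only if these patients are excluded for major deviations.

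**3. The plan's own figure.** Protocol 9.5 gives SD 200 mL and a difference of 93 mL for peak FEV1, two-sided 5%, 80% power. n = 2(1.96 + 0.842)² × 200² / 93² = 72.6, so 73 per group, as stated. The exact t-test power at 73 is 79.7%.

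**4. Number affected, as a ceiling.** Assume that the planned 10% withdrawal gives 8 of 80 per arm, that withdrawals spread evenly over Days 2 to 30, and that every withdrawn patient yields an evaluable EOS curve. Then 8 × 22/29 = 6.1 per arm fall on Days 2 to 23, and 8 × 7/29 = 1.9 on Days 24 to 30.

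**5. Effect on the estimate.** The documents give no SD or target difference for AUC0-12h, so the peak FEV1 values are borrowed. A window starting after day 23 has 72 completers plus 2 late withdrawals, that is 74 per arm. The current rule adds 6, giving 80. Let r be the fraction of the Week 4 effect present in the early curves.

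Expected difference = 93 × (74 + 6r) / 80. Power is for a two-sample t-test, SD 200, two-sided 5%.

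| Rule | n per arm | r | Difference (mL) | Power |
|---|---|---|---|---|
| Week 4 from Day 24 | 74 | n/a | 93.0 | 80.2% |
| Current | 80 | 0 | 86.0 (−7.5%) | 77.2% |
| Current | 80 | 0.5 | 89.5 (−3.7%) | 80.3% |
| Current | 80 | 1 | 93.0 | 83.2% |

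The current rule loses power only when r is below about 0.48. The estimate is biased at any r other than 1, and upward if r exceeds 1. With fewer evaluable EOS curves the effect shrinks; with none it is nil.

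**The case against.** **The rule is a stated convention, not a slip.** SAP 6.4 sends EOS data to the next visit at which the measure is scheduled. An SGRQ-C from Day 2 goes to Week 2 for that reason, and AUC0-12h has no visit between Day 1 and Week 4. This explains the rule, and nothing suggests a typing error. It does not make a Day 3 curve a four-week result. For every other measure with its own window in 6.4, Week 4 starts after day 16 or later.

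**SAP 7.2 is not breached.** A reader might infer that the window contradicts the limit on imputation. It does not: an observed value is assigned to a visit, and nothing missing is filled in. The likeness to a carry-forward is in effect only.

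**Few patients may be affected.** This stands. SAP 16.2.1.1.2 needs data to at least 8 hours. Protocol 3.1 and Table 4 indicate study medication at an early-termination visit, while Protocol 6.6.2 excepts those patients, and 6.6.3 times assessments from the end of dosing without an exception. SAP 16.4 asks only for spirometry: "In cases where patient discontinues early and has spirometry data reported at the EOS visit". The number of post-dose EOS curves therefore cannot be known from the documents, and 6 per arm is a ceiling.

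**No early effect (r = 0) is unlikely.** This also largely stands. Protocol 1.1 reports peak FEV1 gains of 103 and 127 mL over tiotropium plus placebo after 3 days of dosing. Those are not AUC0-12h data, but they point to r well above 0. At r = 0.8 (an assumption) the current rule gives 91.6 mL and 82.1% power.

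**Conclusion.** The point holds as a weakness in the handling of one key secondary endpoint and should be fixed. The main analysis can treat an early curve as a Week 4 result, and the planned LOCF ANCOVA cannot test that handling.

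The consequence is uncertain and probably small. At the ceiling of about 6 per arm, the expected difference falls by at most 7.0 mL (93.0 − 86.0), unless early curves favour placebo. That rests on the borrowed peak FEV1 values, even withdrawal over Days 2 to 30 and an evaluable curve from every withdrawn patient.

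Three stronger readings are not supported:

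- That the primary result is at risk. Peak FEV1 has its own windows, with Week 4 starting after day 23.
- That the rule must dilute the effect or cost power. The bias can go either way, and power rises once r exceeds about 0.48.
- That 6 per arm is an expected count. It is an upper figure under stated assumptions.

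**What to change.** In SAP 6.4, replace the AUC0-12h Week 4 line for the main analysis with the window used for the other spirometry measures: "Week 4 = after day 23 and up to and including day 30". State that earlier EOS AUC0-12h values are used only in the LOCF sensitivity ANCOVA, where SAP 16.4 already carries them to Week 4. The two analyses then treat early discontinuers differently, and the second becomes a test of the first.

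The edit is one line and one sentence. The cost is up to about 6 fewer Week 4 AUC0-12h values per arm. What happens to those patients depends on the model. Under the MMRM of SAP 16.2.2, their Week 4 contribution rests on Day 1 data and a missing-at-random assumption. Under the ANCOVA that SAP 16.3.2 gives for AUC0-12h, used without LOCF, they drop out at Week 4. The SAP should say which model governs the main analysis.

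Separately, Protocol 3.1, 6.6.2, 6.6.3 and Table 4 must be reconciled on study medication at early-termination visits, so that it is clear whether an EOS curve is a post-dose curve. No change to the derivation of peak FEV1 at the EOS visit is proposed here.

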6.5. Statistical Tests and Summaries

In general, unless stated otherwise, continuous variables will be summarized using descriptive statistics (number of patients, mean, standard deviation, median, minimum and maximum values) and for categorical (nominal) variables, the number and percentage of patients will be used.

The default significance level will be 5%; confidence intervals (CIs) will be 95% and all hypothesis testing will be done using two-sided alternative hypotheses, unless otherwise specified.

6.6. Common Calculations

- Change from baseline: Test Value at Visit X – Baseline Value
- Percentage change from baseline:

$$\frac{\text{Test Value at Visit X} - \text{Baseline Value}}{\text{Baseline Value}} * 100\%$$

Document: ...\\Verona_Pharma\\RPL554\\BZA48916\\Biostatistics\\Documentation\\SAP\\Verona CO-205 SAP v1.0

Author: [REDACTED] Version Number: V1.0

Version Date: 05DEC2019

Template No.: CS_TP_BS016 Revision 5

Reference: CS_WI_BS005

Effective Date: 01Apr2018

6.7. Actual Treatment

Once the study unblinds, the patient's actual treatment will be assigned based on the most frequent dose they have received throughout the study. The external vendor, Cenduit, will provide the Material List document after confirmation of a Database Lock. This document will contain the kit numbers, which will be merged with the site data to the dosage that was dispensed at each visit.

If a patient takes more than one dose and the ratio of patient taking them is the same, then assigning actual treatment will follow the two rules:

- RPL554 overrides Placebo
- Higher dose overrides lower dose, i.e. if a patient takes for 50% of the time 1.5 mg dose and for another 50% of the time 0.75 mg dose, then the patient would be assigned 1.5 mg as their actual treatment.

6.8. Software Version

All analyses will be conducted using SAS 9.4.

7. STATISTICAL CONSIDERATIONS

7.1. Adjustments for Covariates and Factors to be Included in Analyses

The following covariates and factors will be used in the analyses. For details of their inclusion in the models, see the specific analysis section.

- Fixed effects: treatment (RPL554 0.375 mg, RPL554 0.75 mg, RPL554 1.5 mg, RPL554 3 mg, Placebo), visit (Day 1, Weeks 1, 2, 3 and 4), visit*treatment, actual reversibility strata (reversible, non-reversible)
- Random effect – patient
- Covariate – baseline

7.2. Missing data

Missing data will only be imputed for the calculation of average (AUC) effects for FEV₁ and FVC, which is described in Section 16.4.

For the sensitivity analysis using analysis of covariance (ANCOVA), missing data will be imputed using the last observation carried forward (LOCF) method prior to analysis described in Section 16.4.

Document: ...\\Verona_Pharma\\RPL554\\BZA48916\\Biostatistics\\Documentation\\SAP\\Verona CO-205 SAP v1.0

Author: [REDACTED] Version Number: V1.0

Version Date: 05DEC2019

Template No.: CS_TP_BS016 Revision 5

Reference: CS_WI_BS005

Effective Date: 01Apr2018

7.3. Multiple Comparisons/ Multiplicity

To address multiplicity in the analysis of the endpoints, statistical testing of the PD parameters and questionnaire scores will be done in a hierarchical order. Firstly, the 3 mg dose will be compared to placebo. If significant then the 1.5 mg dose will be compared to placebo. If found significant, the next lower dose will be compared to placebo. This process will continue until either all doses are compared to placebo, or if one of the comparisons is found to not be significant. There will also be a pairwise comparison between all RPL554 doses, where all doses are compared with each other, as shown in Table 2 in Section 16.1.2.

7.4. Examination of Subgroups

The subgroup analysis will be performed for smoking status, chronic bronchitis and actual reversibility.

The subgroups will be analysed using an MMRM approach, as described in Section 16.1.2 for the primary endpoint, with separate models for the different strata. Reversible patients are those who are reversible to albuterol ($\geq 12\%$ and ≥ 200 mL increase in FEV₁), as defined in Section 5.7 of the study protocol and Section 10 of this Statistical Analysis Plan.

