3.2 Discussion of Study Design, including the Choice of Control Groups

This study aims to determine the effect of RPL554 on the lung function, symptom improvement and safety measures on symptomatic patients with COPD on a stable background of tiotropium.

Twice daily nebulized doses of RPL554 or placebo will be administered for 4 weeks on top of open-label tiotropium. Prior studies have demonstrated that twice daily dosing is appropriate given sustained bronchodilation observed over 12 hours. The treatment duration should allow for evaluation of RPL554 as a maintenance bronchodilator, including peak FEV₁, and the anti-inflammatory response associated with the PDE3/4 dual mechanism of action, as measured by trough FEV₁ and improvement in symptoms. An equal number of reversible and non-reversible patients is planned in order to enrich the population with patients expected to be more responsive to bronchodilator treatment to support optimal dose selection.

A parallel group placebo-controlled design is used to allow for an examination of any dose dependent effects on efficacy and safety compared to placebo. This design makes it possible to obtain unbiased inferences about differences between treatments. Treatments will be administered double-blind with the Investigator and patient unaware of the treatment identity to further minimize any potential bias in the overall assessment of treatment effect and safety.

An eight-fold dose range has been selected in order to show a separation between efficacious and sub-optimal doses.

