Study termination and follow-up will be performed in compliance with the conditions set forth in ICH GCP. The decision to discontinue the study is at the discretion of the Sponsor, the Investigator, the regulatory authority or institutional review board and should if possible be taken by mutual agreement. A record of such a discussion will be prepared and stored in the Study File. The Sponsor will ensure the regulatory authorities and institutional review board are notified.

4.4.5 *Replacement Policy*

It is planned to randomize approximately 400 patients; assuming a 10% early withdrawal rate, it is expected that approximately 360 patients will complete the study. Withdrawn patients may need to be replaced, depending on the actual discontinuation rate.

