5.7 Method of Assigning Patients to Treatment Groups

All patients consented will be assigned a patient identification number upon signing of the informed consent using the following convention: XXX-YYY where XXX is the center number and YYY is the patient number (001, 002, etc.).

Patients will be stratified at randomization according to reversibility testing at Screening, such that all treatment groups will have approximately equal numbers of patients who are reversible to albuterol ($\geq 12\%$ and ≥ 200 mL increase in FEV₁) and those who are not. Each stratum will be capped at 50%. Within each stratum, patients will be equally randomized to one of the four doses or placebo before the first study medication administration at Visit 2. Medication identification numbers will be provided on the study medication kit.

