The standard deviation for peak FEV₁ is estimated to be 200 mL. With a 2-sided test at a 5% significance level and 73 evaluable patients per group, there will be 80% power to detect a true difference of 93 mL between any two treatments. This detectable limit has been considered sufficient to identify an effective dose of RPL554. Assuming a 10% early withdrawal rate, 80 patients per group will be randomized.

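### The SAP fits a separate model in each subgroup stratum and plans no between-stratum comparison, so readers are left to compare significance across strata

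*SAP*

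**What the plan says.** SAP 7.4 names three subgroup factors: smoking status, chronic bronchitis and actual reversibility. Each is analysed with the MMRM of SAP 16.1.2, "with separate models for the different strata". SAP 16.1.2 confirms that the primary analysis is repeated in these subgroups. Its only interaction is treatment by visit, and it reports mean differences with 95% CIs and two-sided p-values. SAP 7.1 lists reversibility as a main effect only, and the ANCOVA and logistic models (SAP 16.2.2, 16.3.2 and 16.5) use it in that way. No treatment-by-subgroup term, test or between-stratum difference appears in either document. SAP 7.4 does not call the subgroup results exploratory and gives no rule for reading them. Protocol section 9 describes no subgroup analysis, so SAP 7.4 and 16.1.2 are the whole specification.

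Reversibility is also the randomisation stratum. Protocol 5.7 caps each stratum at half and randomises equally to the five arms within it. Protocol 3.2 explains that the equal mix is meant to "enrich the population with patients expected to be more responsive to bronchodilator treatment to support optimal dose selection".

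**The concern.** Two separate analyses give two sets of p-values. With no planned comparison, the easiest reading is that the drug works in the stratum that reached significance and not in the other. That inference is unsound, because a difference in significance is not evidence of a difference in effect. With each stratum holding half the patients, the mismatch can arise often when the effects are identical.

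The trial is intended to support Phase III dose selection (Protocol 1.1), and reversible patients are expected to respond more. Results by reversibility will therefore attract attention. What is at stake is a chance pattern being read as a finding about who benefits, or at which dose.

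**Working it through.** **Inputs.**
- Protocol 9.5, variability: the SD of peak FEV₁ "is estimated to be 200 mL".
- Protocol 9.5, target: 73 evaluable per arm, two-sided alpha of 0.05 and 80% power; the size to be detected is "93 mL between any two treatments".
- Protocol 9.5, numbers randomised: "Assuming a 10% early withdrawal rate, 80 patients per group will be randomized".
- Protocol 4.4.5, completers: "it is expected that approximately 360 patients will complete the study".
- Protocol 5.7: two strata of half each, with equal allocation to five arms within each.

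**The plan's own figure.** n = 2 × [200 × (1.96 + 0.8416) / 93]² = 72.6, so 73 per group. Power at 73 is 80.2% by the normal approximation and 79.7% by the noncentral t. The stated figure reproduces.

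**Patients per arm per stratum.** 360 / 5 / 2 = 36, or 73 / 2 = 36.5. The figures below use 36.5; using 36 changes little.

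**Power within one stratum.** SE = 200 × √(2/36.5) = 46.8 mL. Power for 93 mL = Φ(93/46.8 − 1.96) = 51% (50% by the noncentral t; 49% by the t at 36 per arm).

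**Chance of a mismatch when the effect is the same in both strata.** The strata hold different patients, so the two results are independent. With per-stratum power p, the chance that exactly one is significant is 2p(1 − p).

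| Common true effect | p | Exactly one stratum significant |
|---|---|---|
| 93 mL | 0.511 | 50% |
| 103 mL | 0.595 | 48% |
| 127 mL | 0.774 | 35% |

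At 93 mL, both strata are significant in 26% of trials and neither in 24%. The 103 and 127 mL rows use the peak FEV₁ effects that Protocol 1.1 reports for 1.5 mg and 6 mg in the earlier three-day tiotropium add-on study. At 93 mL, varying the SD from 180 to 240 mL gives 47% to 50%.

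In a simulation with 93 mL at every dose, a shared placebo arm and no testing hierarchy, about 89% of trials showed a one-stratum-only result for at least one of the four doses.

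**Smoking and chronic bronchitis.** The documents give no split. Assuming 30/70 to 50/50, the per-dose chance at 93 mL is 55% down to 50%.

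**What a direct contrast would give (reversibility, one dose against placebo).**
- SE of the between-stratum difference = 200 × √(4/36.5) = 66.2 mL (66.7 mL at 36 per arm).
- 95% CI half-width = 1.96 × 66.2 = about 130 mL.
- Difference detectable with 80% power = 2.8016 × 66.2 = about 185 mL.
- Power for a true difference of 93 mL = Φ(93/66.2 − 1.96) = 29%.
- Evaluable patients per arm for 80% power at 93 mL = 4 × 72.6 = about 291, against 73 planned.
- False-difference rate when the strata are identical: 5% per dose, and about 16% for at least one of four doses in the same simulation.

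**The case against.** A reader might infer that the trial cannot say whether reversible patients respond differently. The documents do not support that. The stratum estimates are independent and are reported with CIs, so anyone can form the difference d1 − d2 with SE √(SE1² + SE2²). The contrast is missing from the plan but obtainable from its output. Sample size limits the answer more than model form: even a planned contrast has only 29% power for 93 mL.

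A reader might also infer that the trial was stratified in order to ask whether effect depends on reversibility. No objective or endpoint asks this. Protocol 3.2 gives enrichment for dose selection as the reason, and Protocol 5.7 gives balance between arms.

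Nor does the 50% figure mean that an observed mismatch is probably chance. It assumes identical effects, whereas the protocol expects reversible patients to respond more, so a mismatch could be partly real. At 93 mL the figure is also close to its maximum.

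Further points stand. No passage uses subgroup p-values for a decision. Separate models are defensible, because they let covariance, visit means and baseline slope differ by stratum. Four doses and three factors would give 12 Week 4 contrasts, which itself calls for an exploratory label. The output shells mentioned in SAP 8 were not supplied and might present strata side by side.

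None of this removes the gap. The plan generates stratum-specific p-values and says nothing on how to compare strata.

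**Conclusion.** The point holds as a low-cost improvement to the subgroup section. No between-stratum comparison is pre-specified, and comparing significance across strata is unreliable at these sample sizes. For reversibility, an identical effect in both strata would give a one-stratum-only result about 50% of the time at 93 mL, 48% at 103 mL and 35% at 127 mL, per dose.

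These figures rest on an SD of 200 mL, about 36 evaluable patients per arm per stratum, equal strata, and a simple two-group comparison standing in for the MMRM. For smoking status and chronic bronchitis the size depends on splits that the documents do not give. The primary test uses the whole full analysis set, so neither it nor its error rate is affected.

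**What to change.** In SAP 7.4, for each subgroup factor and each dose against placebo at Week 4, add the between-stratum difference in treatment effect with a 95% CI. There are two ways to obtain it:

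- **Keep the separate models** and report d1 − d2 with SE √(SE1² + SE2²).
- **Fit one MMRM per factor**, adding subgroup, subgroup-by-visit, subgroup-by-treatment and subgroup-by-treatment-by-visit terms, and extend the list of model terms in SAP 7.1 to match.

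Label the subgroup results exploratory, and state that differences between strata are judged from this contrast and not from the separate p-values.

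The cost is a few sentences, a little programming and up to 12 extra estimates, with no new data, visits or patients. The second option assumes a common covariance and baseline slope unless both are allowed to vary by stratum; the first avoids this. Either way precision is low, so the text should say that a non-significant contrast does not show equal response.
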